12. QUALITY CONTROL AND QUALITY ASSURANCE

During study conduct, HealthiVibe will monitor and audit registry data and investigative sites to ensure the protocol, data collection requirements, and applicable research regulations are complied with. The monitors may review source documents to confirm that the data in the registry database are accurate and verifiable. The Investigator must allow HealthiVibe monitors and appropriate regulatory authorities direct access to source documents to perform this verification. These personnel, bound by study participant privacy laws, must maintain the confidentiality of all personal identity or personal medical information (according to confidentiality and personal data protection rules).

The study site may also be subject to review by the IRB, and/or to quality assurance audits performed by HealthiVibe, or companies working with or on behalf of HealthiVibe and/or to inspection by appropriate regulatory authorities.

12.1 Study Monitoring

12.1.1 Responsibilities of the Investigator

The Investigator is required to ensure compliance with all procedures required by this protocol and with all data collection requirements defined by the Sponsor. The Investigator agrees to participate in a site initiation visit and to participate in the required training. The Investigator also agrees to provide reliable data and all information requested by the registry protocol via the most current data collection requirements and any resulting requests for data clarifications in an accurate and timely manner in compliance with the procedures defined by HealthiVibe. The Investigator will also need to provide appropriate training to study participants on how to use the EDC portal for remote data collection at Follow-Up.

The Investigator must also ensure that authorized HealthiVibe representatives are given direct access upon request and sufficient notice to examine, analyze, and verify any source documents that are important to the evaluation and integrity of the registry study.

12.1.2 Responsibilities of the Sponsor

On behalf of the Sponsor, HealthiVibe is responsible for taking all reasonable steps to ensure the proper conduct of the registry protocol with regards to research ethics, compliance, and the standardization, integrity, and validity of the data collected. Thus, the main duty of the monitoring team and other authorized HealthiVibe representatives is to help the Investigator and Sponsor maintain a high level of ethical, scientific, technical, and regulatory quality in all aspects of the registry in accordance with data collection and quality assurance standards for non-interventional, observational registries.

At regular intervals as defined by the registry monitoring plan (RMP), Investigative sites are contacted by HealthiVibe representatives to participate in monitoring visits. These visits are primarily carried out remotely via email, phone, or a virtual meeting space, but may occur on location at a registry site.

Representatives may request to discuss study progress and performance, review compliance with registry evaluation and data collection requirements, verify registry data via source document verification, as well as investigate any emergent data quality issues detected from an aggregate review of data quality indicators.

12.2 Protocol Deviations

Because HealthiVibe registries support human research, HealthiVibe must have written procedures for sites that ensure prompt reporting of deviations. Protocol deviations for non-interventional, observational research are defined as those that may affect the rights or privacy of human subjects or the scientific integrity of the registry's objectives. If a protocol deviation occurs which meets this definition, the registry site will need to complete a protocol deviation form which will be sent to HealthiVibe.

13. ETHICAL AND REGULATORY STANDARDS

13.1 Ethical Principles

HealthiVibe is responsible for ensuring that the study will be conducted in accordance with applicable legal and regulatory requirements, as well as the Guidelines for Good Clinical Practice (International Conference on Harmonization 1996), the Declaration of Helsinki (World Medical Association 2008), and the Health Insurance Portability and Accountability Act of 1996 (HIPAA), where applicable.

The Investigator is responsible for ensuring that the registry is conducted in accordance with the protocol and all applicable local, state, and federal laws and regulations and is responsible for protecting the rights, privacy, and welfare of study participants participating in the registry under his or her care.

In compliance with HealthiVibe public disclosure commitments, this non-interventional study will be recorded in the public registry website clinicaltrials.gov. The registry will contain basic information about the study sufficient to inform interested study participants (and their healthcare practitioners) on how to enroll in the registry.

13.2 Informed Consent

The Investigator or designee must ensure that each study participant is fully informed about the nature and objectives of the registry and possible risks associated with participation, in language and terms the study participant is able to understand. The Investigator or designee will obtain documentation of informed consent from each study participant before any registry evaluation is performed.

The Investigator will retain the original of each study participant's signed ICF. If the study participant is legally blind and/or illiterate, an impartial witness must be present for the consent process and this individual must also sign and personally date the informed consent form.

13.3 Institutional Review Board

It is the responsibility of the Investigator to have prospective approval of the study protocol, protocol amendments, informed consent forms, study participant data collection forms, and other relevant documents (e.g., recruitment advertisements, assessment completion reminders) from the Institutional Review Board (IRB). All correspondence with the IRB should be retained in the site regulatory file. Copies of local IRB approvals should be forwarded to HealthiVibe. Amendments to any documents may not be initiated prior to Sponsor, HealthiVibe, and IRB approval.

14. ADMINISTRATIVE EXPECTATIONS

14.1 Confidentiality

All information disclosed or provided by the Sponsor (or any company/institution acting on their behalf), or produced during the registry, including, but not limited to, the registry protocol, the data collection forms, and informed consent, is confidential. The Investigator and any person under his/her authority agree to undertake to keep confidential and not to disclose the information to any third party without the prior written approval of the Sponsor.

However, the submission of this registry protocol and other necessary documentation to the IRB is expressly permitted, the IRB members having the same obligation of confidentiality.

The Sub-Investigators shall be bound by the same obligation as the Investigator. The Investigator shall inform the Investigator and Sub-Investigators of the confidential nature of the registry.

Furthermore, all Investigators and HealthiVibe agree to adhere to the principles of personal data confidentiality in relation to the study participants, Investigators, and all other collaborators involved in the study.

14.2 Data Protection

The study participant's personal information shall be treated in compliance with all applicable health information privacy laws and regulations. When archiving or processing study participant personal information, HealthiVibe shall take all appropriate measures to safeguard and prevent access to this data by any unauthorized third party.

The same privacy laws and regulations apply to the study participant's clinical data identified by a study participant ID that are stored in the EDC. HealthiVibe shall take all the appropriate measures to ensure that this database is protected and secured from unauthorized disclosure during processing or archiving of clinical database records.

In accordance with applicable research and health information privacy laws, clinical data and personal information collected for this registry are maintained in separate databases for an undefined time period.

HealthiVibe also collects demographic data on Investigators and any person involved in the registry which may be included in a database. Again, HealthiVibe shall take all the appropriate privacy measures to ensure that this information is protected and secured from unauthorized or inadvertent disclosure.

14.3 Study Results

At least thirty (30) days prior to submission for Publication, Investigator shall submit to Nestlé for review and comment any proposed oral or written Publication ("Review Period"). Investigator will consider any such comments in good faith but is under no obligation to incorporate Nestlé's suggestions. The Review Period for abstracts or poster presentations shall be thirty (30) days. If during the Review Period, Nestlé notifies Investigator in writing that: (i) it desires patent applications to be filed on any inventions disclosed or contained in the disclosures, Investigator will defer Publication for a period not to exceed sixty (60) days, to permit Nestlé to file any desired patent applications; and (ii) if the Publication contains Confidential Information as defined in Section 14.1 and Nestlé requests Investigator in writing to delete such Confidential Information, the Investigator agrees to delete such Confidential Information only to the extent such deletion does not preclude the complete and accurate presentation and interpretation of the Study results. Upon request by Nestlé, Investigator shall include an appropriate reference to Nestlé and the Study.

14.4 Registry Termination or Completion

The Sponsor reserves the right to terminate the registry at any time. Both the Sponsor and HealthiVibe have the right to terminate the Investigator's participation in the study according to the registry study agreements.

Appendix A – Eligible PERT

Drug Type	Non-Proprietary Name	Brand Name
Pancreatic Enzyme Replacement Therapy	Pancrelipase	Zenpep®
	Pancrelipase	Creon®
	Pancrelipase	Pancreaze®
	Pancrelipase	Pertzye®
	Pancrelipase	Viokase®

Appendix B – Study Participant Exit Form

What is the reason for the study participant's exit?

- Study participant withdrew from the study
- Study participant was terminated by the Investigator
 - Please specify reason: **[ADD FREE TEXT]**
- Study participant is lost to follow up
- Study participant transferred care to another gastroenterologist
- Data collection period of the registry has ended

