6. STUDY PROCEDURES

6.1 Schedule of Assessments

The registry activities are summarized in the schedule of assessments outlined in **Table 1**.

Table 1. Schedule of Assessments

	Enrollment Day 0	Follow-up direct from study participant ± 7 days		Follow-up on-site (Clinical encounter)	Study participant exit [‡] May occur any time; max. data collection period is 5 years
		Every 3 months	Every 6 months		
Study Participant Provided Data[§]					
Informed consent	X				
Demographic information	X				
Family disease history	X				
Training for remote assessment completion	X				
Height	X				
Weight	X	X			
Current Insurance/work status	X	X			
Current OTC nutritional/herbal supplements	X	X			
Abdominal pain	X	X			
GI symptoms	X	X			
PERT use and treatment satisfaction	X	X			
Dietary habits	X		X		
Health-related quality of life	X		X		
Anxiety/depression	X		X		
Healthcare utilization	X		X		
Investigator Provided Data[*]					
Review/confirm participant eligibility	X				
EPI diagnosis	X				
CP etiology	X				
Medical history	X				
EPI clinical manifestations	X			X	
AEs [•]				X	
Current treatment(s)	X			X	
Reason for exit					X

[§] Study participant provided data will be collected remotely via EDC portal.

^{*} Investigator provided data will be provided during clinical encounters at the registry site. Every 180 days ±30 days with minimum 150 days between visits unless follow-up visit meets criteria for EARLY On-Site Follow-Up (see section 6.3.2)

[‡] Occurs if data collection period has ended or if study participant exits the study due to death, is LTFU, transfers to another gastroenterologist, withdraws from the study or being terminated by the Investigator.

[•] The Investigator will provide information about the occurrence and seriousness of AEs at Follow-up. In the event that an AE is serious, the Investigator will complete an SAE form.

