6.4 Study Participant Exit

A study participant exits the study for one of the following reasons:

- Death
- The study participant withdraws from the study
- The study participant is being terminated by the Investigator
- The study participant transfers to a different gastroenterologist who is not a participating registry site
- The study participant is lost to follow-up (LTFU)
- The data collection period of the registry has ended

A study participant is LTFU when, despite all reasonable efforts (phone calls, email, letters, etc.), contact with the study participant cannot be reestablished, if a study participant does not complete their assessments remotely for 2 consecutive timepoints. This effort must be clearly documented by the HealthiVibe Registry Manager and information about the study participant's vital status (living or deceased) should be documented when known.

The Investigator will document the reason for the study participant's exit using the Study Participant Exit form (see [Appendix B](#)). If the reason for exit is due to death, any associated AEs, and/or AEs occurring after the last follow-up visit should be recorded and reported to HealthiVibe (see [SAFETY REPORTING](#)). The Investigator should carefully choose the option that best reflects the reason for exit at the time; the form should be completed within 5 business days of site awareness of the study participant's exit from the study.

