3.3 Sample Size

Sample size is determined by the investigators' judgment. Target enrollment is approximately 400 study participants with suspected or confirmed EPI. Approximately 20 clinical gastroenterology sites in the United States will be contracted to participate.

Table 1. Schedule of Assessments

	Enrollment Day 0	Follow-up direct from study participant		Follow-up on-site (Clinical encounter) Every 6 months*	Study participant exit [‡] May occur any time; max. data collection period is 5 years
		± 7 days	Every 3 months		
Study Participant Provided Data[§]					
Informed consent	X				
Demographic information	X				
Family disease history	X				
Training for remote assessment completion	X				
Height	X				
Weight	X	X			
Current Insurance/work status	X	X			
Current OTC nutritional/herbal supplements	X	X			
Abdominal pain	X	X			
GI symptoms	X	X			
PERT use and treatment satisfaction	X	X			
Dietary habits	X		X		
Health-related quality of life	X		X		
Anxiety/depression	X		X		
Healthcare utilization	X		X		

USA

	Enrollment Day 0	Follow-up direct from study participant \pm 7 days		Follow-up on-site (Clinical encounter) Every 6 months*	Study participant exit[‡] May occur any time; max. data collection period is 5 years
		Every 3 months	Every 6 months		
Investigator Provided Data*					
Review/confirm participant eligibility	X				
EPI diagnosis	X				
CP etiology	X				
Medical history	X				
EPI clinical manifestations	X			X	
AEs [•]				X	
Current treatment(s)	X			X	
Reason for exit					X

§ Study participant provided data will be collected remotely via EDC portal.

* Investigator provided data will be provided during clinical encounters at the registry site. Every 180 days \pm 30 days with minimum 150 days between visits unless follow-up visit meets criteria for EARLY On-Site Follow-Up (see section 6.3.2)

[‡] Occurs if data collection period has ended or if study participant exits the study due to death, is LTFU, transfers to another gastroenterologist, withdraws from the study or being terminated by the Investigator.

[•] The Investigator will provide information about the occurrence and seriousness of AEs at Follow-up. In the event that an AE is serious, the Investigator will complete an SAE form.

USA

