5 STATISTICAL CONSIDERATIONS AND ANALYSES

5.1 General Considerations

All statistical procedures will be completed using SAS® version 9.4 or higher.

Continuous variables will be summarized using descriptive statistics, including the number of patients with non-missing value (n), mean, median, standard deviation (SD), minimum and maximum. “n” will be presented without a decimal point, minimum and maximum values will be presented with the same precision as in the database, mean and median will be presented with one more decimal place than the minimum and maximum, and SD will be presented with one more decimal place than the mean and median.

For categorical variables, summaries will include counts of patients (frequencies) and percentages. Percentages will be rounded to one decimal place. Descriptive summaries of change from baseline in categorical variables will be provided using shift tables, if applicable.

Day 0 is defined as the date when patients sign ICF.

No data imputation for any missing data will be done in this study.

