5.2 Patient Dispositions

The number (%) of participants in enrolled population will be summarized. The number (%) of screen failures and reasons for screen failures will be provided in the screened population.

The number (%) of participants in the following categories will be provided:

- Participants who completed the study period as per protocol.
 - EOS is the date collected on “Study Participant Exit Form”.
- Participants who did not complete the study period as per protocol and main reason for study discontinuation (“Death”, “The study participant withdraws from the study”, “The study participant is being terminated by the investigator”, “The study participant transfers

USA

to another gastroenterologist”, “The study participant is lost to follow-up”, “Other reasons”).

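### The printed Exit Form (Protocol Appendix B) has no option for death, which Protocol 6.4 lists as an exit reason and SAP 5.2 tabulates

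*Protocol*

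**What the plan says.** Protocol 6.4 lists six exit reasons: death, withdrawal, termination by the Investigator, transfer to a gastroenterologist outside the registry, loss to follow-up, and the end of data collection. It then directs: "The Investigator will document the reason for the study participant's exit using the Study Participant Exit form", pointing to Appendix B. It adds: "The Investigator should carefully choose the option that best reflects the reason for exit at the time". It also has separate instructions on adverse events for an exit caused by death.

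The exit footnote to Table 1 agrees. In the protocol it covers a participant who "exits the study due to death, is LTFU, transfers to another gastroenterologist, withdraws from the study or being terminated by the Investigator"; in the SAP it reads "Occurs if data collection period has ended or if study participant exits the study due to death".

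Appendix B prints one question, "What is the reason for the study participant's exit", and five options: withdrew, terminated by the Investigator (with a free-text reason), lost to follow-up, transferred care, and data collection ended. It prints no option for death, no residual option and no date field.

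SAP 5.2 will report "Participants who did not complete the study period as per protocol and main reason for study discontinuation", with *Death* first among six categories and *Other reasons* last. Under the bullet for completers it says "EOS is the date collected on" the Exit Form. SAP 5.1 adds: "No data imputation for any missing data will be done in this study".

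**The concern.** The form that 6.4 designates for the exit reason cannot, as printed, record one of the reasons that 6.4 lists. An Investigator reporting a death must leave the item blank or pick the nearest wrong option.

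Loss to follow-up is the likeliest substitute. Under 6.4 it applies when a participant misses two consecutive remote timepoints and contact cannot be re-established, and a participant who has died will also miss those timepoints.

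What is at stake is the disposition summary, which Protocol section 11 promises with reasons for dropout. A misfiled death lowers the *Death* row and raises another. A blank that is never queried leaves the reasons short of the total. Either way the disposition table may not match the deaths shown in the safety outputs, and the SAP does not say how such a mismatch would be resolved.

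**Working it through.** The plan states no figure to reproduce, so the check is a comparison of three lists.

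| Exit reason | Protocol 6.4 | Appendix B as printed | SAP 5.2, non-completers |
|---|---|---|---|
| Death | Yes, listed first | **No** | Yes, listed first |
| Withdrawal | Yes | Yes | Yes |
| Terminated by the Investigator | Yes | Yes | Yes |
| Transfer of care | Yes | Yes | Yes |
| Lost to follow-up | Yes | Yes | Yes |
| Data collection ended | Yes | Yes | Not a non-completion category |
| Other | No (the synopsis allows for one) | **No** | Yes |

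- Protocol 6.4 against Appendix B: 6 reasons − 5 options = 1 without an option, namely death.
- SAP 5.2 against Appendix B: 6 categories − 4 matched = 2 without an option, namely *Death* and *Other reasons*.
- Date: SAP 5.2 requires 1 date from the form (EOS); the printed form shows 0.

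**Effect on the table.** If d deaths are filed under another reason, the *Death* count falls by d, the other count rises by d, and the number of non-completers is unchanged. If the d reasons are left blank, the categories sum to d fewer than the non-completers. Assuming the target of about 400 enrolled is the denominator, each such death moves a row by 1/400 = 0.25 percentage points.

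**Whether the deaths survive elsewhere.** Protocol 9.2 makes death an SAE outcome, reportable within 1 business day, and requires sites to request supporting records. Protocol 7.2 includes death as a final SAE status. SAP 5.7 tabulates adverse events leading to death and lists all deaths. The information therefore exists in the database. However, SAP 5.2 does not name the SAE data as a source for disposition and describes no reconciliation.

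**The case against.** The strongest reply is that Appendix B may not be the whole form. SAP 5.2 speaks of a date being collected on it. Protocol section 10 says that the form cites reasons for withdrawal, yet no such field is printed. The appendix still carries a free-text placeholder and shows no participant ID. The live electronic form may therefore already have a death option and a date. This stands as a limit: the point concerns the printed form, and the documents do not settle what was built. It weakens the date point most. It weakens the death point less, because the appendix prints what looks like a closed list that matches 6.4 in every reason but one. If the live form is right, the appendix still misdescribes it.

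Three stronger readings are tempting, and the documents do not support them.

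- *A reader might infer that deaths are lost.* They are not; SAE reporting and the SAP 5.7 listing hold them.
- *A reader might infer that the missing date field undermines an analysis.* The EOS line sits under completers, for whom the end of data collection offers a natural date. SAP 5.2 names the form only for that date; the link between the form and the exit reason comes from Protocol 6.4. No stated output uses an exit date for death, transfer or termination. The form is also due within 5 business days of the site learning of the exit, which limits the uncertainty. Counting the exit reasons that lack a date elsewhere is therefore not a measure of harm.
- *A reader might want to size the problem by projecting deaths.* The Background cites increased mortality in chronic pancreatitis, so some deaths are to be expected, but the documents give no rate. Any projection would rest on assumed rates, and it would count deaths occurring, not deaths misfiled.

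**Conclusion.** The inconsistency is real and should be corrected. One of the six exit reasons in Protocol 6.4 has no option on the printed form, and two of the six non-completion categories in SAP 5.2 cannot be filled from it. The consequence is confined to the descriptive disposition table and its agreement with the SAE and death listings. No estimate, test or interval depends on it.

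This rests on one assumption, that the form is used as printed. The number of exits that would be misfiled cannot be derived from the documents. The date point is secondary: it is a request for confirmation, not a finding that no date is collected.

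**What to change.** 1. Add *Death* and *Other (specify)* to Appendix B. If the live electronic form already has them, correct the appendix to match.
2. Add one sentence to SAP 5.2: exits due to death are reconciled between the Exit Form and the SAE records before database lock. If any exits have already been recorded on the form as printed, include them in that check.
3. Confirm that the live form collects an exit date, and print the field in Appendix B.

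The cost is one appendix or form edit, with the approvals that Protocol 13.3 requires for amendments, and one sentence in the SAP. Participants carry no added burden.
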